#### Secondary Objectives:

1. The proportion of patients in each category according to the ordinal scale at 48 hours and day 7, 14, and 28 after randomization
2. Duration of oxygen therapy
3. Duration of hospital stay
4. The proportion of patients on mechanical ventilation at day 7.(after randomization)

[name] [name], MD  
Additional Professor - Transfusion Medicine  
Institute of Liver and Biliary Sciences  
[name]  
[name]

5. Mortality at day 7 and day 28 (after randomization)
6. Duration of Intensive Care Unit stay
7. Incidence of adverse effects in both groups
8. Presence of antibodies against SARS-CoV-2 in serum on days 0, 3, 7, 14, 21 & 28 after plasma administration, as long as the patient remains in the hospital.
9. Cytokines and acute phase reactants
10. To study the titers in COVID-19 convalescent plasma donors and correlate with duration of illness, the severity of symptoms, duration of hospital stay, drugs used in therapy, duration between recovery, and donation.

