**Antibody Titers of Convalescent Plasma and Patients Plasma by ELISA****For Donors:**

The titre of serum neutralizing antibody which is the spike protein antibody, directed against the SARS-CoV-2 RBD (receptor binding domain) proteins. The titre will be done by IgG ELISA or by Rapid IgG antibody titre. The minimum titre of 80 is needed for the use of convalescent in patients.

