**For recipients:****1. Real-time PCR for SARS-CoV-2:**

Nasal swab samples will be taken prior to transfusion and tested for SARS-CoV-2 by real-time PCR method. The test should be positive for eligibility of the recipient along with clinical criteria for COVID-19.

2. Antibody titre: The serum of each recipient will be obtained and IgG antibody titre by enzyme-linked immune-sorbent assay (ELISA) or Rapid IgG antibody method will be tested one day prior to the convalescent plasma transfusion. Changes of IgG antibody titre before and after convalescent plasma transfusion in patients will be studied. The serum will be stored for neutralizing antibody titers by plaque reduction will be done subject to availability.

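### Antibody sampling is timed from plasma administration, which controls never receive, so the stated before/after titre change cannot separate donor antibody from the patient's own response

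*Protocol*

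**What the plan says.** Under Secondary Objectives, item 8 reads: "Presence of antibodies against SARS-CoV-2 in serum on days 0, 3, 7, 14, 21 & 28 after plasma administration". Its timing clause in full is "after plasma administration, as long as the patient remains in the hospital", so sampling continues only while the patient is an inpatient. In the same list, ordinal-scale category (item 1), mechanical ventilation (item 4) and mortality (item 5) are timed from randomization, for example "Mortality at day 7 and day 28 (after randomization)". Item 7 covers "Incidence of adverse effects in both groups"; item 8 has no such wording.

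The For recipients section says that "IgG antibody titre by enzyme-linked immune-sorbent assay (ELISA) or Rapid IgG antibody method will be tested one day prior to the convalescent plasma transfusion". It then states the contrast of interest: "Changes of IgG antibody titre before and after convalescent plasma transfusion in patients will be studied".

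The Intervention section gives controls standard of care without plasma. The section on transfusion of convalescent plasma specifies two doses on consecutive days.

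**The concern.** A between-arm comparison needs a time origin that both arms have. Plasma administration occurs in one arm only. Followed as written, the text tells a site when to bleed a plasma patient but not when to bleed a control.

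The one contrast described in words is a change across transfusion. Every enrolled patient has PCR-confirmed infection and can make antibody during the same days, so that change does not measure what plasma added. The randomized control arm could supply the missing part, but only if it is sampled on the same clock.

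At stake is the interpretation of the planned measure of patients' antibody response. The primary endpoint and the clinical secondary outcomes are not touched.

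**Working it through.** The protocol gives no figure for the antibody outcome, so there is nothing to reproduce. The check is of the text, followed by two illustrations on assumed inputs.

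**1. Time origin**

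| Item | Counted from | Exists in controls? |
|---|---|---|
| Ordinal scale, ventilation, mortality (items 1, 4, 5) | Randomization | Yes |
| Antibody days 0–28 (item 8) | Plasma administration | No |
| Baseline titre (For recipients) | One day before transfusion | No |

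The two antibody entries also disagree. Item 8 implies a day-0 baseline, while For recipients places it a day earlier. With doses on two consecutive days, the text does not say which dose defines day 0.

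**2. What the before/after change contains**

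Let D be the change due to donor antibody and E the change from the patient's own response.

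- Before/after in recipients: D + E.
- Same interval in controls: E.
- Plasma minus control: (D + E) − E = D, taking E as unaffected by plasma. If plasma alters the patient's own response, the difference is the total effect of assignment to plasma.

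Only the last line isolates the effect of plasma, and it needs control samples on a shared clock.

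**3. Selection by stopping at discharge**

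Assumptions, none from the protocol:
- True prevalence p of antibody is equal in the two arms.
- Daily discharge hazard is 0.075 if antibody positive, and 0.05 if negative in controls.
- Plasma multiplies the hazard in antibody-negative patients by h.

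Observed prevalence among inpatients on day t = p·exp(−0.075t) / [p·exp(−0.075t) + (1 − p)·exp(−0.05ht)].

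For p = 0.6 and t = 14:
- Controls: 0.2100 / (0.2100 + 0.1986) = 51.4%.
- Plasma, h = 1.3: 0.2100 / (0.2100 + 0.1610) = 56.6%.
- Plasma, h = 1.5: 0.2100 / (0.2100 + 0.1400) = 60.0%.

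| True prevalence | Spurious difference, h = 1.0 | h = 1.3 | h = 1.5 |
|---|---|---|---|
| 40% | 0 | 4.7 points | 8.0 points |
| 60% | 0 | 5.2 points | 8.6 points |
| 80% | 0 | 3.9 points | 6.2 points |

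The artefact is smaller early on. For p = 0.6 and h = 1.5, the plasma arm shows 60.0% at every t:
- Day 3 controls: 0.4791 / (0.4791 + 0.3443) = 58.2%, a difference of 1.8 points.
- Day 7 controls: 0.3549 / (0.3549 + 0.2819) = 55.7%, a difference of 4.3 points.

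The denominators give the share of controls still in hospital: 82%, 64% and 41% at days 3, 7 and 14.

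**4. Precision of a between-arm comparison**

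Allocation is 150 to 50 (protocol). Two-sided α = 0.05, 80% power and the control rates are assumptions. Power = Φ[(d − 1.96·SE₀)/SE₁], with SE₀ from the pooled rate and SE₁ from the separate rates.

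Example: control rate 60%, d = 0.203, 50 v 150. Pooled rate = (50 × 0.600 + 150 × 0.803)/200 = 0.752; SE₀ = 0.0705; SE₁ = 0.0765; (0.203 − 0.1382)/0.0765 = 0.847; power = 80%.

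| Control rate | All sampled (50 v 150) | Half still inpatients (25 v 75) |
|---|---|---|
| 40% | 22.6 points | 31.2 points |
| 60% | 20.3 points | 27.0 points |
| 80% | 14.4 points | 18.1 points |

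Entries are the smallest detectable difference in antibody presence.

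**5. Assay**

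The sentence that governs patients' samples is in For recipients: ELISA or a rapid IgG method. The parallel sentence "The titre will be done by IgG ELISA or by Rapid IgG antibody titre" stands under For Donors and concerns release of plasma. The heading over the donor text names ELISA only, for patients' plasma as well. Nothing requires one method across a patient's serial samples or across arms, and nothing says that the two read on the same scale.

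**The case against.** The strongest reply is that nothing says controls go unsampled. The analysis bullets under Flow Chart name Mann-Whitney, chi-square and Fisher tests, which compare independent groups, and no paired test is listed. The recipients' section also contains the eligibility PCR that every patient needs, so its title need not mean the plasma arm alone. The case report form is listed as an annexure but not shown, and could hold a control schedule. All of this stands. A reader might infer that the control arm is left unused for this outcome; the text does not support that. It does support a narrower statement: the time origin, baseline and contrast that the protocol states are all defined by transfusion. Independent-group tests do not supply the missing day 0.

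Three other inferences go too far:
- That this is the trial's only evidence on mechanism. Item 9 covers cytokines and acute phase reactants, and stored serum may be tested for neutralizing antibody, subject to availability.
- That nearly every patient would show a rise that is then credited to plasma. No figure supports the first part, and no section makes the attribution.
- That assays will be mixed. The text permits this but does not plan it.

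In-hospital sampling is also a reasonable concession to feasibility. In the illustration it produces no difference between arms unless plasma changes discharge differently by antibody status. That limits the claim about bias, but the later samples still come from a selected group.

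**Conclusion.** The point holds for a secondary outcome and should be corrected. The antibody schedule rests on an event that one arm never has, the two descriptions of baseline differ, and day 0 is ambiguous between two doses. A before/after change in recipients therefore cannot be read as the effect of plasma. This is not detail left for an analysis plan: the protocol itself fixes the origin and the end of sampling, and control samples that were never drawn cannot be recovered at analysis.

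The missing control origin carries the point. Truncation at discharge is secondary. Its illustrated size, 0 to 8.6 points at day 14, depends wholly on assumed hazards, prevalence and a differential effect of plasma on discharge. The detectable differences of 14.4 to 31.2 points rest on an assumed α, power and control rate. The assay choice is the weakest part.

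**What to change.** - Take the baseline serum before randomization in every patient. Count days 3, 7, 14, 21 and 28 from randomization in both arms, in item 8 and in For recipients alike. This removes the conflict over baseline and the question of which dose is day 0.
- Record the date and time of each transfusion. The protocol does not give the interval from randomization to the first dose, and the day-3 result has to be read against it.
- Use the same assay for all of a patient's samples and in both arms.
- Make the between-arm comparison at days 3 and 7, adjusted for baseline, the antibody analysis.
- Keep later inpatient-only samples as descriptive, reporting by arm how many patients were sampled, discharged or dead at each day.

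The cost is a wording change and some extra inpatient blood samples in controls, with no new visits and no change to treatment.

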#### **Treatment Centres**

**Lok Nayak Jai Prakash Hospital (LNJP)**

**Rajiv Gandhi Super-speciality Hospital**

#### **B) Methodology**

##### **Donor Plasmapheresis**

COVID-19 recovered patients will be counseled and informed regarding convalescent plasma donation. The contact information of those who agree will be sent to the coordinator at ILBS Blood Centre.

- The prospective donor will be contacted and if willing to come for donation, the donor will be provided conveyance if required, to come to ILBS Blood centre for Plasma Donation
- At ILBS the donor will be counseled and the doctor in-charge will explain the procedure to the Donor.
- The donor will be given a Donor Information Sheet and Informed consent will be taken on the document
- The eligibility for plasma donation will be ascertained through Medical History, Physical Examination, and laboratory tests.

### Donor Eligibility for Plasmapheresis

- Virologically documented (PCR positive by nasopharyngeal swab) who is recovered and free of symptoms for 14 days.
- Has tested negative for SARS CoV 2 on two consecutive tests 24 hrs apart.
- Fulfill all criteria of donor eligibility for donor Plasmapheresis under the Drugs & Cosmetics Act 1940 and Rules 1945, amended 11.03.2020
- Females who have been pregnant may be tested for anti-HLA antibodies and eligible if negative for the same.

### The following Donors will be excluded

- Do not fulfill all criteria of donor eligibility for donor Plasmapheresis under the Drugs & Cosmetics Act 1940 and Rules 1945, amended 11.03.2020
- Females who have been pregnant and have not been tested for HLA antibodies or are HLA antibody positive if tested and previously transfused donors (to prevent TRALI)
- Donors who have taken steroids during treatment for COVID-19

### Donor Selection Process

- A detailed medical history of the donor will be taken and documented
- Physical examination ( Height, Weight, Blood Pressure, Temperature, adequate veins for phlebotomy)
- Laboratory Testing: complete Blood count, Testing for hepatitis B virus, hepatitis C virus, HIV, malaria, and syphilis) by serology, blood grouping, and antibody screening. Serum protein will be done in repeat donors ( Ref: D&C Act and Rules)
- Serum COVID-19 specific IgG antibody positive (with an IgG titre higher than 80).
- All Results Evaluated & Clinically Correlated

The donor is deemed eligible/non-eligible

### Plasmapheresis Procedure

- Determine Volume to be collect-approx. 500 ml
- As per the Drugs & Cosmetics Act 1940 and Rules 1945, amended 11.03.2020
- Start Donor Plasmapheresis Procedure(As per SOP)
- Collect Convalescent Plasma

The convalescent plasma will be properly labeled and frozen at  $-80^{\circ}\text{C}$  in a separate Deep Freezer. It will not be issued to other patients who are with non-COVID.

- **Label Details:** As per the Drugs & Cosmetics Act 1940 and Rules 1945, amended 11.03.2020.
- **Storage condition-** Below  $-30^{\circ}\text{C}$
- **Shelf life:** - 1 Year

[name] [name], MD  
Additional Professor - Transfusion Medicine  
Institute of Liver and Biliary Sciences  
[name]  
[name]

**Other Sources of Convalescent Plasma:**

**Convalescent Plasma collected during a CP donation drive by Delhi Govt. following all rules and regulations of the Drugs & Cosmetics Act 1940 and Rules 1945, amended 11.03.2020 is stored at ILBS and will be used in this trial.**

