**The tests for Donors:****1. Real-time PCR for SARS-CoV-2:**

Nasal swab samples will be taken prior to donation and tested for SARS-CoV-2 by real-time PCR method if the donor does not have two negative reports 24 hrs apart.

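### Stored plasma from the government donation drive is committed to the trial with only the Drugs & Cosmetics Act named as a condition, and nothing ties it to the trial's own donor rules on recovery time, PCR clearance, HLA antibody, transfusion history and steroids

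*Protocol*

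**What the plan says.** All references are to Section 13 of the protocol unless stated otherwise.

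- **Second source.** *Other Sources of Convalescent Plasma* describes plasma collected in a Delhi Government donation drive "following all rules and regulations of the Drugs & Cosmetics Act 1940 and Rules 1945, amended 11.03.2020 is stored at ILBS". The same sentence commits it to the trial without further qualification: "amended 11.03.2020 is stored at ILBS and will be used in this trial".
- **Donor eligibility.** *Donor Eligibility for Plasmapheresis* lists the Act as one bullet: "Fulfill all criteria of donor eligibility for donor Plasmapheresis under the Drugs & Cosmetics Act 1940 and Rules 1945, amended 11.03.2020". Beside it stand separate bullets for 14 symptom-free days after recovery from PCR-documented infection, HLA-antibody status of previously pregnant donors, and PCR clearance: "Has tested negative for SARS CoV 2 on two consecutive tests 24 hrs apart".
- **Donor exclusions.** *The following Donors will be excluded* again gives the Act its own bullet. It separately excludes previously pregnant donors who are HLA-untested or positive and previously transfused donors, with TRALI prevention as the stated purpose. It also excludes "Donors who have taken steroids during treatment for COVID-19".
- **Fallback PCR.** For donors without two negative reports, *The tests for Donors* provides: "Nasal swab samples will be taken prior to donation and tested for SARS-CoV-2 by real-time PCR method".
- **Titre.** *Donor Selection Process* requires "Serum COVID-19 specific IgG antibody positive (with an IgG titre higher than 80". The ELISA section, under *For Donors*, says: "The minimum titre of 80 is needed for the use of convalescent in patients".

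**The concern.** If compliance with the Act were equivalent to trial eligibility, the extra bullets would be redundant. The protocol lists them separately, so it treats them as additions to the Act. The drive stock is introduced with the Act alone. Read as written, a drive unit could be issued in line with the *Other Sources* paragraph although its donor would have been refused under the trial's own lists.

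Two things are at stake. The first is recipient safety, because one of the rules not tied to this stock was written to prevent TRALI. The second is the safety estimate. *Justification for Unequal Allocation* gives additional safety information on plasma as the reason for the 3:1 ratio, and that estimate could pool two products whose donors were screened differently. The body of the protocol does not ask for the source to be recorded per unit.

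A smaller consequence concerns secondary objective 10. It correlates donor titres with illness duration, severity, drugs used and the recovery-to-donation interval. The protocol does not say whether these data exist for drive donors.

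**Working it through.** The point rests on a comparison of text. The protocol gives no figure to reproduce.

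**Step 1. Rule by rule: does the text apply it to the stored drive units?**

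| Rule | Where stated | Applied to drive stock? | Route for units already stored |
|---|---|---|---|
| Drugs & Cosmetics Act and Rules | Eligibility list, exclusion list, *Other Sources* | Yes, the only condition stated there | Already asserted |
| 14 symptom-free days | Eligibility list | Not stated | Donor record only; no check described |
| Two negative PCR tests 24 h apart | Eligibility list | Not stated | Donor record only; the fallback swab is taken before donation |
| HLA antibody (previously pregnant donors); previous transfusion | Eligibility list (HLA), exclusion list (both) | Not stated | Pregnancy and transfusion history from the donor record; no check described |
| Steroids during COVID-19 treatment | Exclusion list | Not stated | Donor record only; no check described |
| IgG titre | *Donor Selection Process*; ELISA section | Yes, through the minimum of 80 for use in patients | No step described for titrating stored units |

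**Step 2. Titre.** The ELISA section's minimum is a condition on use in patients and is not limited by source, so it covers drive units. Two loose ends remain. No titration step for stored units is described. The two statements also disagree at one value: a titre of exactly 80 fails a requirement to be higher than 80 but meets a minimum of 80.

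**Step 3. Scale.**

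- Planned treatment arm: 150 patients (*Sample Size calculation*). Doses per patient: 2 (*Intervention*). Doses needed: 150 × 2 = 300.
- Share of those doses from the drive: not stated, so anything from 0 to 300.
- Related serious adverse events in Table 2 (Section 10): 4 + 7 + 11 + 3 = 25, of which TRALI is 11, the largest group.
- TRALI rate in Table 2: 11 / 5,000 = 0.22% (95% CI 0.12% to 0.39%). Applied to 300 doses, this gives 300 × 0.0022 = 0.66 expected events, with a range from 300 × 0.0012 = 0.36 to 300 × 0.0039 = 1.17. This assumes that the rate is per transfusion and carries over to this trial.

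Table 2 does not show how donor HLA screening changes that rate, so these figures give scale only. They do not measure the harm from the gap.

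**The case against.** The strongest reply is that the *Other Sources* paragraph describes how the drive plasma was collected and waives nothing. The exclusion list is headed without exception, and the donor tests and the titre minimum come after the second source has been introduced. One can therefore read every donor rule as applying to every donor. The content of the Act and Rules is not reproduced. Nor are Annexure 4 (donor selection and procedure) and Annexure 6 (additional donor information), any of which may overlap with the trial rules. The absolute TRALI rate is also low.

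Much of this stands. There is no explicit waiver, the drive donors' actual status is unknown, and no effect can be sized. The reply does not close the gap, however. The eligibility list sits within a procedure for prospective donors who come to ILBS for plasmapheresis. The drive stock has its own heading and names only one of the listed criteria. The fallback PCR cannot be carried out after the plasma has been stored.

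Three stronger readings are tempting and are not supported:

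- **That low-titre or antibody-free units could be issued, so that a null result could not be interpreted.** The minimum titre for use in patients excludes such units whatever their source.
- **That potency and safety become uncontrolled.** The titre floor and the Act's donor rules still apply.
- **That treatment hospitals could issue drive units on their own account.** The stock is held at ILBS, and Section 8 has plasma thawed on requisition and sent to the treating centre.

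**Conclusion.** The concern holds in a limited form. The protocol commits stored drive plasma to the trial with the Act as the only stated condition, while its own donor lists treat the Act as one requirement among several. The recovery-interval, PCR, HLA/transfusion and steroid rules are not tied to that stock anywhere in the document. Titre is covered, apart from the missing titration step and the disagreement at exactly 80.

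The consequence is a possible mix of differently screened products in the arm that was enlarged to study safety. Its size is unknown: up to 300 doses could be involved, or none, and the drive donors may all have met the trial rules. The conclusion assumes that the separately listed bullets are meant to add to the Act, as their layout implies, and that the annexures not reproduced here do not already settle the matter. The point should be resolved before any drive unit is issued, because per-unit source and donor history are harder to reconstruct afterwards.

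**What to change.** - Reconcile *Other Sources of Convalescent Plasma* with the eligibility list, the exclusion list, *Donor Selection Process*, *The tests for Donors* and the ELISA section, so that one set of donor and unit requirements governs all plasma used in the trial. Which requirements those are is for the investigators to decide.
- State how compliance of units already stored is documented: which donor-record items are checked, and how the titre is established.
- Reconcile the two titre statements so that a value of exactly 80 has one status.
- Record the source of each unit on the transfusion monitoring form (Annexure 7), if it is not already there, and report adverse events by source.

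**Cost.** Protocol wording, a donor-record check, and an assay already in use for donors. Some stored units may prove unusable. How many cannot be judged, because the protocol gives neither the size of the stock nor the state of its records.

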**The tests for Donors:****1. Real-time PCR for SARS-CoV-2:**

Nasal swab samples will be taken prior to donation and tested for SARS-CoV-2 by real-time PCR method if the donor does not have two negative reports 24 hrs apart.

**Antibody Titers of Convalescent Plasma and Patients Plasma by ELISA****For Donors:**

The titre of serum neutralizing antibody which is the spike protein antibody, directed against the SARS-CoV-2 RBD (receptor binding domain) proteins. The titre will be done by IgG ELISA or by Rapid IgG antibody titre. The minimum titre of 80 is needed for the use of convalescent in patients.

